3.4 Sample size and source of subjects

A total of **35 analyzable patients** will be recruited for participation and the study will be performed at a single-center institution, Brigham and Women's Hospital (BWH). BWH Faulkner Hospital, Newton Wellesley Hospital, and Massachusetts General Hospital, MGH (PI: [name]) will participate as feeder sites. All dermatology clinical assessments will be conducted through the Center for Clinical Investigation (CCI) at the BWH or at the [name] dermatology clinics. All patients will be referred for cardiac PET imaging to BWH, with BWH serving as the Core Imaging Lab and Data Coordinating Center.

4. SUBJECT ENROLLMENT

4.1. Procedures for obtaining informed consent

The Lead Investigator or one of the co-investigators/research assistants will obtain consent during the study-related hospital visit prior to any study-related procedures. Consent of subjects who do not speak English will be obtained and documented following the procedures outlined by IRB policy. The informed consent process will also be documented and added to the patient information for this study.

4.2. Methods of Enrollment

Potential study subjects will be recruited from the dermatology clinic at BWH with external advertising at the Dermatology sites throughout New England. We will include de novo external advertising and social media advertisements, such as the Rally research advertising website through Partners Healthcare.

Screening procedures will include queries for potentially eligible subjects from lists of patients who are followed by BWH Dermatology. BWFH and MGH will also be added as referring sites. This will NOT include any patients who have OPT-OUT of the new RODY program at MGB. We will perform an RPDR query for patients who are eligible for this RODY program at BWH, BWFH, and MGH. The RPDR query will be performed by searching for patients with at least 2 ICD codes for psoriasis in the last 24 months. Exclusion criteria will include ICD diagnosis codes for rheumatoid arthritis, which is a common autoimmune disease that is an exclusion for the study, and known coronary artery disease. We will then screen these MRNs by chart review to further filter and only send to eligible patients after review of the clinical record. All visits will still occur at BWH.

If patients are deemed eligible, we will use two mechanisms to contact. The primary method that we will use the OPT OUT RODY program upon which after obtaining the necessary regulatory approval patients will be contacted with an IRB letter through Patient Gateway or mail. The second method is physicians at MGB will be contacted personally and/or via e-mail to explain the purpose of the study, review its potential risks and discomforts, and the evaluation of whether a patient might be a candidate for the study. After a patient's physician agrees to have a patient participate in the study, the physician will initially introduce the study to the patient in order to obtain the patient's permission to be contacted by study staff. If the patient agrees, the referring physician will provide the study staff with the patient's contact information. This will allow the study staff to call the patient to explain the study and provide the patient a copy of the informed consent form.

Patients who agree to participate will be scheduled for the screening visit, at which point the PI or a qualified member of the research team will review the informed consent form with the patient and answer any additional question the patient may have. Treatment assignment and monitoring will be

performed at the BWH Dermatology clinic. All cardiovascular imaging-related procedures will take place at BWH.

4.3. Treatment assignment

Study subjects will receive a total of three doses of 100mg of SC Tildrakizumab. Each dose will occur on weeks 0, 4 and 16, respectively.

3. STUDY PROCEDURES

5.1. Study visits and parameters to be measured

A detailed description of the assessments that will occur at each visit is presented in Table 1.

Table 1. Schedule of Assessments

Procedure	Screening (-60 to -1 days)	Baseline Dermatology visit (day 0)	Baseline Cardiac PET/Echo (day 0)	Dermatology Visit #2 (week 4)	Dermatology Visit #3 (week 16)	End of Treatment Cardiac PET/Echo and Derm visit #4 (week 24)
Informed Consent	X					
Inclusion/Exclusion Criteria	X		X			
TB Screening	X					
Demographics	X					
Medical History	X		X	X	X	X
Medication History	X		X	X	X	X
Vital Signs	X		X	X	X	X
Physical Exam	X		X			X
Full skin exam	X	X		X	X	X
Pregnancy Test	X		X			X
Lab Tests	X		X			X
ECG			X			X
PET/CT			X			X
Echocardiogram			X			X
Study Drug Dispensed		X		X	X	

AE Monitoring		X	X	X	X	X
---------------	--	---	---	---	---	---

*NOTE: The baseline visit (Day 0) and the End of Treatment Visits (Week 24) can be combined into one visit or separated into two visits each within a week period.

Screening Visit (-60 to -1 days)

- All screening assessments will occur within 30 days prior to start of medication
- Obtain informed consent
- Obtain medical history, including demographics, overview of significant past or present illnesses by body system, as well as a complete cardiac and surgical history
- Obtain concomitant medications review
- Obtain vital signs, including weight and height, systolic and diastolic blood pressure (BP), heart rate (HR), and oxygen saturation (O₂ sat)
- Complete physical exam
- Skin assessment: PGA, BSA, PASI)
- Perform laboratory tests, including serum pregnancy test
- TB screening performed per protocol as discussed in Appendix 2

Study Visit 1: Baseline (Day 0, prior to first dose)

- Verify clinical stability
- Confirm that subjects have withheld caffeine for 12 hours and fasted for 4 hours prior to imaging tests
- Confirm that subjects have withheld beta blockers, calcium channel blockers and arterial vasodilators for 24 hours prior to the PET scan
- Obtain interim medical history and concomitant medications review
- Obtain vital signs, including weight and height, systolic and diastolic blood pressure (BP), heart rate (HR), and oxygen saturation (O₂ sat)
- Obtain 12-lead ECG
- Complete physical exam clinical stability since screening evaluation
- Perform laboratory tests, including serum pregnancy test prior to any imaging
- Perform PET/CT scan
- Perform echocardiogram
- Dermatology Psoriasis baseline clinical visit with full skin assessment (PGA, BSA, PASI)
- Remind patients on most common side effects of the new drug. They are encouraged to immediately contact study investigators/staff by email and/or phone for any new or concerning symptoms.
- Provide first dose of Tildrakizumab 100mg sc

Study Visit 2: Week 4 (study visit #2)

- Verify clinical stability
- Obtain interim medical history and concomitant medications review

- Obtain vital signs, including weight and height, systolic and diastolic blood pressure (BP), heart rate (HR), and oxygen saturation (O₂ sat)
- Full psoriasis skin assessment, including PASI, BSA and PGA scores
- Monitor for AE; subjects are again educated about the most common side effects. They are encouraged to immediately contact study investigators/staff by email and/or phone for any new or concerning symptoms.
- Provide second dose of Tildrakizumab 100mg sc

Study Visit 3: Week 16 (study visit #3)

- Verify clinical stability
- Obtain interim medical history and concomitant medications review
- Obtain vital signs, including weight and height, systolic and diastolic blood pressure (BP), heart rate (HR), and oxygen saturation (O₂ sat)
- Full psoriasis skin assessment, including PASI, BSA and PGA scores
- Monitor for AE; subjects are again educated about the most common side effects. They are encouraged to immediately contact study investigators/staff by email and/or phone for any new or concerning symptoms.
- Provide third dose of Tildrakizumab 100mg sc

Study Visit 4: Week 24 (End of Treatment, study visit #4)

- Verify clinical stability
- Obtain interim medical history and concomitant medications review
- Obtain vital signs, including weight and height, systolic and diastolic blood pressure (BP), heart rate (HR), and oxygen saturation (O₂ sat)
- Complete physical exam
- Full psoriasis skin assessment, including PASI, BSA and PGA scores
- Monitor for AE; subjects are again educated about the most common side effects. They are encouraged to immediately contact study investigators/staff by email and/or phone for any new or concerning symptoms.
- Perform laboratory tests, including serum pregnancy test prior to any cardiovascular imaging
- Perform Cardiac PET/CT scan
- Perform echocardiogram

Telephone follow-up call

Contact all subjects by telephone approximately 2-3 days after the Study Visit 4 to ensure no adverse events have occurred since the study visit.

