3. SUBJECT SELECTION

3.1. Study Design

Open label, single-center, single arm pilot study. Patients with moderate-to-severe psoriasis and evidence of cardiovascular risk factors will be recruited from Skin and Related Musculoskeletal Diseases Clinic and the Rheumatology Clinic from the Brigham and Women's Hospital. After giving written informed consent to participate in the study and fulfilling criteria for inclusion, patients will be scheduled for baseline cardiac PET/CT, echocardiogram and dermatology visit. On the day of the cardiovascular testing, patients will undergo rest and vasodilator-stress PET/CT scan for measurement of CFR at baseline), and again after completion of 24 weeks of therapy as well as echocardiogram. Labs will be drawn at the baseline visit and at the 24-week final cardiovascular visit. The baseline and follow-up cardiovascular visits will be scheduled within +/- 7 days of the Dermatology clinic visits for feasibility to allow patient and departmental coordination. Patients will be encouraged to remain on stable medical therapy throughout the enrollment period.

3.2. Study group:

In order to target a higher-risk population, we will enroll patients with evidence of moderate-to-severe psoriasis, which is the most closely linked to increased cardiovascular risk^{13,64,65}. We plan to target patients at heightened cardiovascular risk and coronary microvasculature dysfunction. In order to maintain feasibility, inclusion criteria will include *at least one* of the following: presence of DM, metabolic syndrome, or elevated hsCRP>mg/dl. We chose to use the cut-off of hsCRP \geq 2mg/dl which has been used as a cut point in large-scale clinical trials, including the CANTOS trial. CANTOS was the first trial in cardiology to show that in patients with a history of MI and elevated hsCRP \geq 2mg/dl, treatment with

canakinumab resulted in a reduction in recurrent cardiovascular events compared to placebo^{66,67}. Similarly, metabolic syndrome and DM are both well-known cardiovascular risk factors and studies from our research group have demonstrated reductions in CFR. Reduced CFR, which reflects coronary microvascular dysfunction, was further shown to be associated with major adverse cardiovascular events (MACE) across the spectrum of metabolic disease⁶⁸.

3.2.1. Inclusion criteria:

- Moderate-to-severe psoriasis
- Ages 18-90

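### No pregnancy test is scheduled at weeks 4 and 16, when doses 2 and 3 are given; a pre-dose test there is a cheap safety improvement

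*Combined protocol and SAP*

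**What the plan says.** Section 4.3 fixes the dosing: "Each dose will occur on weeks 0, 4 and 16, respectively". In section 5.1, the Table 1 row "Study Drug Dispensed" is marked at the baseline dermatology visit, week 4 and week 16. The pregnancy-test row is marked at screening, the baseline cardiac PET/echo visit and week 24. At weeks 4 and 16 both the pregnancy-test row and the laboratory row are empty.

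The visit lists in section 5.1 agree with the table:

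- Visit 1, headed as taking place before the first dose: "Perform laboratory tests, including serum pregnancy test prior to any imaging".
- Visit 2 (week 4): no pregnancy or laboratory test, then "Provide second dose of Tildrakizumab 100mg sc".
- Visit 3 (week 16): no pregnancy or laboratory test, then "Provide third dose of Tildrakizumab 100mg sc".
- Visit 4 (week 24), where no drug is given: "Perform laboratory tests, including serum pregnancy test prior to any cardiovascular imaging".

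Section 5.4 describes the baseline and end-of-treatment tests as being for women of child-bearing potential ahead of each PET scan. On timing, section 3.1 (Study Design) says "The baseline and follow-up cardiovascular visits will be scheduled within +/- 7 days of the Dermatology clinic visits", and the Table 1 note says the day 0 and week 24 visits "can be combined into one visit or separated into two visits each within a week period".

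Pregnancy and breastfeeding are exclusions (sections 3.2.2 and 7.6). Section 9.4.7 has a pregnancy that arises during dosing, or within 30 days after it stops, reported and followed as though it were an SAE.

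**The concern.** The plan keeps pregnant women out at entry and treats a pregnancy under dosing as a serious matter, but it does not check pregnancy status again before it re-doses. A woman who conceives after the baseline test and does not yet know it can receive dose 2, dose 3 or both while the schedule is followed exactly. The checks at weeks 4 and 16 (clinical stability, interim history, adverse events) bring out only a pregnancy she already recognises. The week 24 test can detect an ongoing pregnancy, but by then all three doses have been given. What is at stake is avoidable exposure of a pregnancy to study drug. No estimate or test of the primary endpoint is involved.

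**Working it through.** **Inputs.** Doses at weeks 0, 4 and 16 (section 4.3), which are days 0, 28 and 112. On-study pregnancy tests at baseline and week 24 (Table 1 and the visit lists), nominally days 0 and 168. A window of 7 days either way between cardiovascular and dermatology visits (section 3.1, Study Design). The plan states no figure for these gaps, so there is none to reproduce.

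**Last scheduled test to dose** (dose day minus test day).

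- Dose 1: 0 − 0 = 0 days. The Visit 1 list places the test before this dose.
- Dose 2: 28 − 0 = 28 days.
- Dose 3: 112 − 0 = 112 days.
- With the baseline PET visit, and so the test, on day −7: 28 + 7 = 35 and 112 + 7 = 119 days.

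**Dose to next scheduled test** (test day minus dose day).

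- After dose 2: 168 − 28 = 140 days.
- After dose 3: 168 − 112 = 56 days.
- With the week 24 PET visit on day 161 or day 175: 133 to 147 days after dose 2, and 49 to 63 days after dose 3.

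**Longest gap between on-study tests.**

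- Now, nominal: 168 − 0 = 168 days.
- Now, with the window at its widest (tests on days −7 and 175): 175 + 7 = 182 days.
- With tests added on days 28 and 112, nominal: gaps of 28, 84 and 56 days, so the longest is 84.
- With the added tests and the same widest window: 28 + 7 = 35, then 84, then 175 − 112 = 63 days. The longest is still 84.

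**Against the plan's own reporting window.** If dosing is taken to stop with dose 3 on day 112, the section 9.4.7 window closes on day 112 + 30 = 142. After baseline, no scheduled test falls inside it; the next is nominally on day 168, which is 26 days later.

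**Number of added tests.** Taking 35 as the number enrolled (section 6.1), the ceiling is 2 × 35 = 70. The real number is lower, because only women of child-bearing potential need the test.

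**The case against.** The strongest reply is that the plan is more careful than a quick look at Table 1 suggests. A reader might infer that testing serves the scan alone, or that no dose is covered because no Table 1 column carries both a pregnancy test and a dose. The documents do not support either reading. The screening test has no scan attached and serves eligibility, and the Visit 1 list puts the baseline test before dose 1. The empty overlap in the table arises because day 0 is split into two columns that may be one visit. Two doses lack a same-visit test, not three.

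A reader might also infer known fetal harm, or a material number of exposed pregnancies. The documents give no reproductive data for tildrakizumab, no number of women of child-bearing potential and no conception rate. In a study of about 35 patients aged 18 to 90, that number may be small. The case is therefore precautionary. It rests on the plan's own exclusion and its handling of pregnancy, not on a measured risk.

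Nor can it be said that the plan has no way to stop dosing. Section 9.3 allows discontinuation for a serious adverse event, for jeopardized health or at the investigator's decision. These routes would serve once a pregnancy is known, but they do not detect one. Section 9.1 speaks of laboratory tests at each visit, but it does not mention pregnancy tests and does not fill the gap in the visit lists.

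Contraception would be the main control. The protocol text available contains no such requirement, but the consent pages were removed, so its absence cannot be presumed. Even where contraception is used, a pre-dose test adds a check.

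Finally, the remedy is partial. A very early conception can be missed at either visit. One that occurs between weeks 4 and 16 would not be tested for until week 16, when only dose 3 can still be withheld.

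**Conclusion.** The omission is real and consistent across Table 1, the Visit 2 and Visit 3 lists and section 5.4, so it is not an effect of a broken table. Followed as written, the plan gives doses 2 and 3 at 28 and 112 days after the last scheduled test (up to 35 and 119 days), and schedules the next test only after dosing has ended. These figures assume visits on their nominal days, apart from the stated 7-day window, and a baseline test done before dose 1 as the Visit 1 list requires. The change is worth making because it costs very little and fits the plan's own stance on pregnancy. It is a participant-safety improvement; the primary analysis, power and sample size are unaffected, and no count of affected patients is claimed.

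**What to change.** 1. In Table 1, mark the pregnancy test at weeks 4 and 16 for women of child-bearing potential.
2. In the Visit 2 and Visit 3 lists, add a urine pregnancy test ahead of the dose, with a negative result required before the drug is given. Urine is suggested because no blood draw is scheduled at these visits.
3. In section 5.4, extend the trigger so that the test is done before each PET scan and before each dose.

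Optionally, name pregnancy among the discontinuation criteria in section 9.3. This is a clarification, since a known pregnancy already has routes to stopping.

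The cost is two point-of-care tests per eligible woman, at visits that already take place, and a few lines of protocol text. No extra visit or invasive procedure is needed.

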5.2. Concomitant medications

Only patients with moderate-to-severe psoriasis will be included in the study. Because concurrent medications can potentially affect coronary blood flow and flow reserve (e.g., antihypertensive and oral hypoglycemic agents), only patients on stable treatment for hypertension and diabetes will be included in the study. The following medications will be allowed provided they are neither initiated nor discontinued during the study period:

- Aspirin;
- Angiotensin-converting enzyme inhibitors and/or Angiotensin Receptor Blockers;
- β -blockers;
- Nitroglycerin and long-acting nitrates;
- Oral anti-diabetic medications and Insulin;
- Stable hormone replacement therapy

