with psoriasis without obstructive coronary artery disease who were clinically referred for cardiac PET testing have a high prevalence of coronary microvasculature dysfunction and a significant reduction in CFR compared to matched controls ([name] et al., *submitted American College of Cardiology (ACC) abstract 10/2019*). Furthermore, these findings highlight the importance of further mechanistic studies on whether reducing systemic inflammation in patients can lead to improved myocardial blood flow, tissue perfusion, and endothelial function.

Anti-inflammatory therapies can modulate CFR. There is preliminary evidence that anti-inflammatory therapies lead to improved CFR. Indeed, treatment with statins in patients with dyslipidemia has been shown to improve CFR in a way that is modified among carriers of a specific polymorphism that reduces IL-1 β expression³⁶. Short-term inhibition of IL-1 activity with the IL-1 receptor antagonist anakinra in rheumatoid arthritis patients without perfusion abnormalities has been shown to improve echocardiographic measures of LV myocardial deformation (by speckle tracking) and CFR (by Doppler flow velocity in the left anterior descending artery (LAD))³⁷. Finally, treatment with methotrexate led to reduced clinical scores of disease severity and improved CFR (as measured by echo Doppler flow velocity in the LAD) in patients with early rheumatoid arthritis, with no effect on common carotid intima-medial thickness³⁸.

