- Body surface area (BSA) involvement $\geq 3\%$ **or** 5-point Physician Global Assessment (PGA) Score ≥ 3 **or** Psoriasis Area and Severity Index (PASI) Score ≥ 12
- Patients who have failed biologic therapy, topical steroids, phototherapy, or other systemic therapies will be required to have a wash-out period, which will be calculated accordingly to the specific drug (Appendix 1).
- Evidence of at least one cardiovascular risk factor which includes hsCRP ≥ 2 mg/L, DM, obesity (BMI >25), hyperlipidemia, hypertension, family history of early coronary artery disease, or evidence of metabolic syndrome
 - Metabolic syndrome defined as at least three of the following: glucose ≥ 100 mg/dl or taking hypoglycemic agent, HDL <40 mg/dl (men) or 50 mg/dl (women), triglycerides ≥ 150 mg/dl, waist circumference >40 in mean or >35 in women, or blood pressure $\geq 130/85$ or taking anti-hypertensive.
- If the patient is on a statin therapy, they must be on a stable dose for at least 6 months prior to enrollment.

3.2.2. Exclusion criteria:

- Documented history of other systemic inflammatory diseases, including SLE and RA, which in the opinion of the investigator would be inappropriate for enrollment.
- Prior history of untreated chronic infection (tuberculosis (Appendix 2), severe fungal infection, or known HIV positive, chronic hepatitis B or C infection), history of active solid malignancy, myeloproliferative or lymphoproliferative disease within 5 years, excluding treated non-melanoma skin cancer
- Renal insufficiency (CrCl <40 ml/min)
- NYHA class IV heart failure
- Patients requiring chronic treatment with oral prednisone >10 mg/day, methotrexate, or other immunosuppressive agents.
- Pregnancy and Breastfeeding

There are certain vaccines, such as live attenuated vaccines, that are an exclusion for the study. This includes MMR, rotavirus, smallpox, chickenpox and yellow fever. The COVID-19 vaccine can be received while on study (<https://pubmed.ncbi.nlm.nih.gov/33549649/>, <https://pubmed.ncbi.nlm.nih.gov/33422626/>). As part of the screening process, we will confirm that potential subjects are not scheduled to receive one of the above live attenuated vaccines while on study and if so, they will be excluded from participation.

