5.4. Data to be collected and timing of data collection

At each of the study visits, a medical history with symptom assessment, medication review, vital signs, and physical exam will be obtained. As described above, additional data from the PET/CT scan and echocardiogram will be obtained at baseline and at the end of treatment period. One week after completion of the trial, telephone follow-up will be conducted to assess for any adverse events.

Laboratory analysis: Routine labs required for initiation and monitoring of biologic therapy will be collected at the baseline and follow-up cardiovascular visit. At the Baseline and End of Treatment visit, hs-CrP, Hs-troponin, BMP, CBC, lipid panel, and a pregnancy test (women of child-bearing potential before

each PET scan) will be obtained. Inclusion criteria will include TB screening per protocol. Blood samples will also be collected and stored for future analysis of biomarkers of inflammation and myocyte injury.

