9. MONITORING AND QUALITY ASSURANCE

9.1. Safety monitoring

The PI of the study will monitor the overall safety of the study and will report any adverse effect to the IRB immediately. The PI will also monitor this study to ensure that subjects' human rights, safety, and well-being are protected, that the study is properly conducted in adherence to the current protocol, and study data reported by the investigator/subinvestigator are accurate, complete and verifiable with study-related records such as source documents.

Safety data will be obtained at each study visit from the spontaneous reports by patients of adverse events, vital sign monitoring, physical examinations, 12-lead ECGs and clinical laboratory tests. In addition, telephone follow-up will be conducted to assess for any adverse events. All safety data will be reviewed by the principle investigators of the study (which includes two clinical cardiologists and two clinical dermatologists)

Patients with unexpected abnormalities on the baseline PET scan will be discussed with the patient's PCP/Dermatology physician to decide whether the patient should participate in this pilot trial. The findings will be discussed with the patient and the patient's primary physician in order to facilitate an appropriate management plan. If a patient is excluded on safety grounds, we do not think that this will affect our ability to determine the effect of Tildrakizumab on myocardial blood flow.

The safety of Tildrakizumab will be assessed with respect to the following end points: (1) death from any cause, (2) the composite of death from any cause or any cardiovascular hospitalization, (3) frequency of symptomatic documented arrhythmia, (4) serious adverse events related to the study drug and clinically significant laboratory abnormalities.

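### Section 5.2 does not hold statins and other lipid-lowering drugs constant between the two PET scans, so a CFR gain from one would be credited to tildrakizumab; the likely effect is small and cheap to prevent

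*Combined protocol and SAP*

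**What the plan says.** Section 5.2 gives its reason first: "concurrent medications can potentially affect coronary blood flow and flow reserve". It admits only patients on stable treatment for hypertension and diabetes, and then sets the rule: "The following medications will be allowed provided they are neither initiated nor discontinued during the study period". The list names aspirin, ACE inhibitors or ARBs, beta-blockers, nitrates, diabetes drugs including insulin, and hormone replacement. No lipid-lowering drug appears.

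Statins are mentioned in two other places. Section 1, on anti-inflammatory therapy and CFR, states that "treatment with statins in patients with dyslipidemia has been shown to improve CFR". The inclusion criteria in 3.2.1 state: "If the patient is on a statin therapy, they must be on a stable dose for at least 6 months prior to enrollment". For the period on study, Section 3.1 says only: "Patients will be encouraged to remain on stable medical therapy throughout the enrollment period".

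The risk factors that qualify a patient under 3.2.1 include diabetes and "hyperlipidemia, hypertension, family history of early coronary artery disease, or evidence of metabolic syndrome". Being on a statin is not required. Section 5.4 schedules a lipid panel: "At the Baseline and End of Treatment visit, hs-CrP, Hs-troponin, BMP, CBC, lipid panel, and a pregnancy test". Under 9.1, unexpected abnormalities on the baseline PET lead to a discussion of whether the patient should take part, and then: "The findings will be discussed with the patient and the patient's primary physician in order to facilitate an appropriate management plan".

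The design is a single arm (3.1). The primary analysis is a paired t-test on the change in CFR (6.4), with no rule for patients whose background drugs change.

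**The concern.** The list applies the plan's own principle, that drugs able to move CFR should not change between the scans. By that principle statins belong on it, because Section 1 credits them with moving the primary endpoint. The existing statin rule ends at enrolment and says nothing about a patient who is not yet on one. A patient who qualifies through hyperlipidemia and takes no statin can enter, start one after the baseline PET, and break no stated rule.

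A control arm would absorb such changes if they were equally common in both arms. This trial has none, so the paired t-test attributes the whole change to tildrakizumab. For a statin started or increased, the error runs in one direction, towards an apparent benefit.

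**Working it through.** **Reproducing the plan's figure.** Section 6.2 gives SD 0.7 at each scan, correlation 0.7, baseline mean 2.4, a 15% effect (0.15 × 2.4 = 0.36) and two-tailed alpha 0.05.

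- SD of change = √(2 × 0.7² × (1 − 0.7)) = √0.294 = 0.542.
- Exact paired t-test power for 0.36 is 90.2% with 26 pairs, matching the 26 in Table 2. The other eight cells of Table 2 also match. No stated figure is in dispute.

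**Completers.** Section 6.1 says that 35 includes 20% attrition, so 35 × 0.8 = 28. Sections 3.4 and 6.2 call the 35 analyzable or evaluable, so 35 is shown as well. The standard error of the mean change is 0.542/√28 = 0.102, or 0.542/√35 = 0.092.

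**Assumptions, because the documents give neither value.** Let f be the share of completers who start a statin between the scans: 1 in 28, 5% or 10%. Let g be the CFR gain per starter at week 24: 0.12 to 0.36, that is 5% to 15% of 2.4. The top value equals the trial's whole target effect and serves as an upper bound.

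**Formulas.** Bias in the mean change = f × g. SD of change with a mixture of starters and non-starters = √(0.542² + f(1 − f)g²). The rejection rate with an inactive study drug comes from the noncentral t distribution with n − 1 degrees of freedom, at the two-sided 0.05 critical value.

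| f | g | bias | share of 0.36 | two-sided, n = 28 | upper tail, n = 28 | two-sided, n = 35 |
|---|---|---|---|---|---|---|
| 1/28 | 0.12 | 0.004 | 1% | 5.02% | 2.75% | 5.02% |
| 1/28 | 0.36 | 0.013 | 4% | 5.17% | 3.29% | 5.21% |
| 5% | 0.12 | 0.006 | 2% | 5.04% | 2.85% | 5.05% |
| 5% | 0.36 | 0.018 | 5% | 5.32% | 3.66% | 5.41% |
| 10% | 0.12 | 0.012 | 3% | 5.15% | 3.24% | 5.18% |
| 10% | 0.36 | 0.036 | 10% | 6.28% | 5.18% | 6.62% |

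The plan's test is two-tailed, so the two-sided columns compare with 5%. The upper tail compares with 2.5% and is the chance of a false claim of improvement. If nobody starts, the bias is zero.

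**What a check without the starters can show.** Leaving out 3 of 28 patients moves the mean by chance alone with SD 0.542 × √(1/25 − 1/28) = 0.035. The bias from 3 starters at the upper bound is 3/28 × 0.36 = 0.039, about the same size. Leaving out 1 gives a chance SD of 0.542 × √(1/27 − 1/28) = 0.020 against a bias of 0.004 to 0.013. In a simulation with an inactive drug, leaving out the 3 patients with the lowest baseline CFR shifted the mean by −0.041, through regression to the mean. Power for 0.36 is 92.3% with 28 pairs, 91.3% with 27 and 89.0% with 25.

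**The case against.** The strongest reply is that the effect is hypothetical and very small. Both inputs are assumed, and with up to 5% starting the two-sided error stays between 5.0% and 5.3%. Giving every starter the full gain is also generous, since some would have had only weeks of treatment by the second scan. The Section 1 sentence goes on to say that the statin effect varies with an IL-1β polymorphism, and the title of its reference describes young healthy men. All of this stands and limits the size of the point.

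The plan also has safeguards. An unexpected baseline PET abnormality prompts a decision on participation (9.1). Section 9.3 lists six grounds for discontinuation, including non-compliance and jeopardised health. Medications are reviewed at baseline and at weeks 4, 16 and 24 (Table 1), so a start would be recorded. These soften the gap. None of them forbids a statin start or says how such a patient is analysed.

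Section 5.2 could be read as a closed list that bars every unlisted drug. That fails for statins, because 3.2.1 admits statin users.

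Three stronger readings are tempting, and the documents do not support them:

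- A reader might infer a serious false-positive risk. If 30% started and each gained 0.48, the two-sided rate with 28 completers would be 24.1%. Nothing in the documents supports that start rate, and a gain of 0.48 exceeds the trial's own target.
- A reader might infer that abnormal baseline findings routinely lead to a statin in a patient who stays in the trial. Section 9.1 puts a participation decision before the management plan, and the documents do not say that lipid results go to the treating physician.
- A reader might infer that an analysis without the starters would settle the matter. The chance variation shown above rules that out.

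**Conclusion.** The gap is real and minor. Section 5.2 leaves out a drug class that the protocol itself says improves the primary endpoint, and no other section prevents a statin from being started or increased between the scans. In a single-arm paired comparison that gain is credited to tildrakizumab.

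If up to 10% start and gain 0.12 to 0.36 each, the mean change is inflated by at most 0.036, a tenth of the target. The two-sided type I error is 5.0% to 6.3% with 28 completers, and at most 6.6% with 35. These figures rest on assumed start rates and gains and on the plan's SD and correlation. The case for acting is that an existing rule has an avoidable hole. The documents do not show that the primary result is in serious danger.

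**What to change.** **Section 5.2.** Add statins and other lipid-lowering drugs to the list. State that they are not started, stopped or changed in dose between the two PETs, except where the treating physician judges that the change cannot wait until the week 24 scan, and that the date of any change is recorded. Section 1 speaks only of statins; including the other lipid-lowering drugs is a precaution. Add calcium channel blockers too: they are withheld for 24 hours before each PET (5.3) but are also missing from the list.

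**Section 6.4.** Keep every patient with both PETs in the primary paired t-test. Beside it, as a prespecified descriptive check, report the result without patients who changed a lipid-lowering or other flow-active drug, including calcium channel blockers, after the baseline PET.

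**Cost.** A short addition to 5.2 and one extra result, using medication histories already collected. The sample size and primary test do not change, and urgent treatment is not blocked. The exception means that some starts may still occur. The check has slightly lower power (about 89% to 91% for 0.36 with 25 to 27 pairs, against 92% with 28) and may be biased downward by about 0.04 if starters have low baseline CFR. It cannot by itself confirm or exclude a bias of this size, so it should not replace the primary result.
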